Aim 1 will compare the percent change in anxiety (STAI) from baseline between the three study groups at one month (T1) and 1 year (T3) following notification. Assuming the percent change may likely range from -100% to +100% (range of 200 percentage points), we conservatively assume a standard deviation of 50 percentage points (range/4) in the percent change measure. We will have 80% power (along with 1.7% type-I error rate) to detect a difference of 9.3 in average percent change between any two of the groups with a two-sample t-test at T2 with 600 per group. At T3, we will have 80% power to detect a difference of 10.6 (466 per group).

The second outcome will be knowledge regarding breast density, measured ordinally as the number correct of 3 key items (range 0-3 correct). This will be tested with pairwise Wilcoxon rank-sum tests, for which the null hypothesis is that the probability of someone answering more items correctly in one group versus another is 0.5 (i.e. equal chance). At T2, with 600 women per group, we will have 80% power (along with 1.7% type-I error rate) to detect a probability of 0.554 or more between any two of the groups. At T3, we will have 80% power to detect a probability of 0.561 (466 per group).

Aim 2 will compare adherence to next routine screening mammogram between the three notification groups. This outcome "adherence to next annual screening" is pertinent to all 2,000 women and will be obtained via EMR. A sample size of 666 in each group will yield 80% power to detect a difference of 9 percentage points between any two of the groups (type-I error rate 1.7%) based on a chi-square test.

Aim 3 will qualitatively analyze documentation provided by the *promotora* after each patient interaction in the interpersonal study group. Based on the recommendation of Morse,¹¹⁹ we will have ample data from over 600 patient-*promotora* interactions to capture a range of responses. Furthermore, this large sample size will offer the opportunity to qualitatively examine the type of information exchanged for particular subgroups of patients, such as Spanish-speaking only, those receiving notification that they have dense breasts, and those receiving notification that they do NOT have dense breasts. The analysis of Aim 3 qualitative data will provide a rich resource for informing the design of targeted educational materials for specific populations and developing generalizable tools to enhance communication about appropriate risk-based screening for breast cancer.

Data Analysis Plan:

Analytic Approach for Specific Aim 1

This Aim will compare anxiety as well as knowledge gained between breast density notification approaches (usual care, enhanced, interpersonal). Anxiety will be measured using the state anxiety scale within the State Trait Anxiety Inventory (STAI). Items within this scale are rated on a 0 to 3 Likert-type scale and scores are calculated as the sum of the items. The possible scores can range from 0-60, with higher scores indicative of greater anxiety. To adjust for baseline anxiety levels, we will calculate the percent change in anxiety from baseline at each follow-up: $100 * (\text{follow-up anxiety} - \text{baseline anxiety}) / \text{baseline anxiety}$. We hypothesize that there will be less increase in anxiety for the interpersonal group as compared to the enhanced or usual care groups. The percent change will be compared between the three notification study groups with pairwise t-tests at one month as well as at one year following notification. To account for three pairwise comparisons within each time point, P-values less than 0.017 will be considered statistically significant, to preserve an overall type-I error rate of 0.05 within each time point.

Knowledge regarding breast density will be measured as the number of statements answered correctly as previously described. The number of items answered correctly (range of 0-3) will be compared between the three notification groups with pairwise Wilcoxon-rank-sum tests at one month as well as at 1 year following notification. We assume that baseline knowledge will be similar between the groups due to randomization, and we hypothesize that knowledge will be greater in the interpersonal group as compared to the enhanced or usual care groups. To account for three pairwise comparisons within each time point, P-values less than 0.017 will be considered statistically significant, to preserve an overall type-I error rate of 0.05 within each time point.

Analytic Approach for Specific Aim 2

This Aim will compare adherence to next routine screening mammogram between breast density notification approaches (usual care, enhanced, interpersonal). This information will be obtained from the EMR. The percentage of women who adhere to their next routine screening mammogram will be compared between the three notification groups with pairwise chi-square tests. We hypothesize that women randomized to the interpersonal group will be more likely to adhere to next screening mammogram relative to either the usual care or enhanced study groups. To account for three pairwise comparisons P-values less than 0.017 will be considered statistically significant to preserve an overall type-I error rate of 0.05

Analytic Approach for Specific Aim 3

Framework analysis will be used to understand and analyze the qualitative data provided by the *promotora*. This approach is based in content analysis and allows for *a priori* themes to be identified and categorized as well as *de novo* themes that emerge through inductive analysis. The process begins with familiarization in which the content and range of responses is examined. Next, a thematic framework is generated by identifying key issues, concepts, and themes which will be used to reference the data. We anticipate that issues regarding understanding MBD, supplemental breast screening, and breast cancer risk will arise in the data, but emerging issues will also be captured. Finally, the analytic framework will be applied

to the narrative data, which will be indexed using NVivo (NVivo 10, QSR International Pty Ltd.). All NVivo datafiles are housed behind the Mayo Clinic firewall. Subsequently, the research team will review the audio-recorded *promotora*-patient interactions and apply the analytic framework to them using NVivo in order to triangulate the perspective of the *promotora* and observation of the intervention's delivery by the study team.

Analytic Approach for Exploratory Aim 1

There are no standard approaches to performing a financial evaluation of *promotora* interventions; a systematic review identified only 6 studies that provided economic analyses of community health worker interventions, with insufficient evidence to conclude a cost benefit. The time spent by the *promotora* contacting and educating each patient randomized to the interpersonal study group about her breast density results will be recorded, and the mean *promotora* time per patient will be estimated. The prevailing hourly salary plus benefits will be used to estimate the mean cost of *promotora* time per patient.

Analytic Approach For Exploratory Aims 2 and 3

We will test each hypothesis using multivariate regression analyses, adjusting for relevant confounders. We will also explore differences in perceived risk, risk communication, and preferences for informed decision-making using chi-square tests.

List of Attachments (Documents to be found in IRBe)

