This research addresses the following "big-picture" questions: "Is the density notification law recently adopted in AZ having the intended impact on patients receiving mammography at a Federally Qualified Health Center (FQHC)?" and "Are there positive or negative unintended consequences to this legislation?" We hypothesize that sending standard-language (as determined by legislators) notification about breast density along with a woman's mammogram results is a sub-optimal method of notification. Further, we hypothesize that the goals of educating women about their breast density, (including the impact that dense breast tissue can have on mammogram sensitivity and overall risk of breast cancer) and encouraging a discussion with their health care provider about breast cancer screening options, may not be achieved by sending written notification in the absence of additional efforts to educate women about breast density. We propose to answer these questions by conducting a 3-arm randomized trial. All arms will receive the standard density notification letter, but 2 arms will also receive educationally-enhanced notification about breast density. Thus, the 3 study arms are:

usual care (standard density notification only), enhanced (standard density notification + written educational materials on breast density), and interpersonal (standard density notification + written educational materials on breast density + verbal interaction with a *promotora*/health educator).

The impact of this research can only increase as additional states mandate that women attending mammography screening (many of whom have never heard of breast density before) receive written notification about their breast density and its role in breast cancer risk. Particularly in FQHC's and other community settings where breast imaging experts may not be on staff and patients may have limited English proficiency, lower health literacy, and fewer economic resources, it is critical that density notification occur in ways that optimize receptivity and comprehension, minimize anxiety and worry, and enhance self-efficacy and intention to continue screening and pursue supplemental breast screening, if appropriate.

Aims, purpose, or objectives:

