All consented patients will be asked to complete a baseline (T1) survey [Attachment 6] that includes: demographic characteristics; breast density risk factors (parity, age at menarche, menopausal status, hormonal contraceptive use, breastfeeding, and age at first birth); Family history of breast cancer; and mammography screening history (approximate lifetime number of mammograms, number of times recalled, number of breast biopsies). The primary outcome measure for Aim 1 is anxiety. Anxiety will be measured using the state anxiety subscale of the State-Trait Anxiety Inventory (STAI). This measure was selected because of its known psychometric properties, its use in the mammography literature, and our own experience with its use in an intervention study involving Latinas attending cancer screening. Additional psychosocial measures will include health literacy, cancer fatalism, self-efficacy to return for mammography at the next screening interval, breast cancer worry, perceived risk of breast cancer using numerical, verbal and comparative estimates, and the Patient-Reported Outcomes Measurement Information System (PROMIS) measure (short form) addressing depressive symptoms. Knowledge will be assessed using two previously developed items for the national survey regarding density as an independent risk factor and as having a masking effect as well as additional items derived from the written education materials. Our selection of short form assessments where available carefully balances capturing a comprehensive set of important psychosocial measures while reducing respondent burden. We have chosen published measures with favorable psychometric properties and use existing measures where available. Administering the depression measure from the PROMIS Initiative (www.nihpromis.org) will utilize an important resource for validated patient-reported outcomes (PROs) and position our study results within a larger, cross-institute NIH initiative. Based on our experience at MPHC, an interviewer-facilitated mode of survey completion is preferred by patients over self-administered surveys and results in higher quality data. We will provide paper surveys in English and Spanish; participants can mark their own answers or follow along and mark their answers as questions are read to them by the CRC. We anticipate the study assessments will take approximately 30 minutes to complete. The study coordinator will review the responses to the PROMIS items related to depression following completion of the T1 survey. Based on the responses, the study coordinator will follow the steps in the Plan for Depression Questions [Attachment 18]. If the plan

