Follow-up (T2) Assessment. Participants will be contacted by study staff using Mayo Clinic or Mountain Park telephone that will display the Mountain Park phone number.[Attachment 8] approximately 2 weeks after patients have their mammogram to complete a follow-up survey [Attachment 9]. If the study staff is unsuccessful in reaching the participant by telephone, the T2 survey will be mailed to the participant with a cover letter [Attachment 10] and return postage-paid envelope. If the patient has not actively refused or withdrawn, or completed the T2 assessment, study staff will attempt to follow-up by telephone. Study staff may also send a certified letter asking the participant to call them and schedule a time to complete the survey (see Attached reminder letter). If telephone and mail contacts are not successful, participants will be coded in RAVE as a non-responder at T2. The CRC will collect the data over the telephone and mark the answers on a paper survey for double data entry by the Survey Research Center (SRC). The CRC will ask questions designed to measure acceptability of the method by which women received their breast density results and satisfaction with the content and clarity. Knowledge will be re-assessed using the same items described in the baseline assessment. Women will be queried about their own breast density as a check that the mailed notification was read and processed. Anxiety, depressive symptoms, perceived risk of breast cancer, self-efficacy, and breast cancer worry measures administered at baseline will be repeated. Behavioral intention to return for a screening mammogram at the recommended interval will also be assessed. All women will be asked if they discussed their breast density with their health care provider. Women with dense breasts will be asked if they discussed supplemental screening options with their health care provider (e.g., breast ultrasound, MRI). Questions will address whether each of these activities occurred, and if not, whether they are pending (requested by the patient). If not requested, intentions regarding these behaviors will be measured. The study coordinator will review the responses to the PROMIS items related to depression following completion of the T2 survey. Based on the responses, the study coordinator will follow the steps in the Plan for Depression Questions [Attachment 18]. If the plan calls for study personnel to contact the patient, she will do so in accordance with the Plan for Depression Questions and using the Script for Depression Questions Follow-up [Attachment 19].

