
Follow-up (T3) Assessment. Participants will be contacted by study staff using Mayo Clinic or Mountain Park telephone that will display the Mountain Park phone number.[Attachment 11] approximately 1 year after patients have received their mammogram results to complete the third survey [Attachment 12]. Reminder calls and a T3 survey mailing with cover letter [Attachment 13] will follow the procedures outlined for the T2 assessment. Study staff may also send a certified letter asking the participant to call them and schedule a time to complete the survey (see Attached reminder letter). Study staff may also approach patients in clinic if they present to the mammography unit for screening.. If telephone, in-person and mail contacts are not successful, participants will be coded in RAVE as a non-responder at T3. The T3 assessment will include repeated measurement of anxiety, depressive symptoms, breast cancer worry, perceived risk, and discussion of their breast density with their health care provider. It will include questions regarding information seeking about the topic of breast density and re-assess breast density knowledge. Intentions regarding future utilization of mammography and supplemental breast screening will be measured. Attendance at mammography will be queried to capture self-reported screening behavior that may have occurred elsewhere and would not be documented in the MPHC EMR; however this is unlikely because many patients receive low-cost mammography through special programs at MPHC. All women will be queried at the T3 assessment about their attendance at mammography; these self-report data

will be corroborated with EMR data. Women who indicate they received a mammogram elsewhere will be asked where and when this occurred. The study coordinator will review the responses to the PROMIS items related to depression following completion of the T3 survey. Based on the responses, the study coordinator will follow the steps in the Plan for Depression Questions [Attachment 18]. If the plan calls for study personnel to contact the patient, she will do so in accordance with the Plan for Depression Questions and using the Script for Depression Questions Follow-up [Attachment 19].

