We will manage the study data using RAVE and REDCap databases designed specifically for the study. These systems are located behind the Mayo Clinic firewall. Users must have a Mayo Clinic provided ID/password to connect to the databases and their ID must be specifically authorized in order to access study data. Only the PI can grant such authorization. The tools are HIPAA-compliant, can be set up to use branching logic and field validation to help improve the accuracy of data entry, and the data can be easily exported for statistical analysis. Administration of survey assessments (T1, T2, and T3) will occur by telephone and be interviewer-facilitated by the bilingual CRC. Surveys will be

kept secure in a locked file cabinet until they are sent in batches to Rochester for data entry by the Survey Research Center.

(1a) This is a multisite study involving Mayo Clinic and non Mayo Clinic sites. *When checked, describe in detail the research procedures or activities that will be conducted by Mayo Clinic study staff.*

(1b) Mayo Clinic study staff will be engaged in research activity at a non Mayo Clinic site. *When checked, provide a detailed description of the activity that will be conducted by Mayo Clinic study staff.*

The study will be conducted at Mountain Park Health Center and Mayo Clinic Staff will be consenting and following the patient throughout the study through patient contact and through medical records.

Subject Information

Target accrual is the proposed total number of subjects to be included in this study at Mayo Clinic. A "Subject" may include medical records, images, or specimens generated at Mayo Clinic and/or received from external sources.

Target accrual: 2,000

Subject population (children, adults, groups): Adult women presenting for a screening mammogram

Inclusion Criteria:

Speak English or Spanish

Women between the ages 40 and 74

Exclusion Criteria:

Age less than 40 or 75+

Research Activity

Check all that apply and complete the appropriate sections as instructed.

- Drug & Device:** Drugs for which an investigational new drug application is not required. Device for which (i) an investigational device exemption application is not required; or the medical device is cleared/approved for marketing and being used in accordance with its cleared/approved labeling. (Specify in the Methods section)
- Blood:** Collection of blood samples by finger stick, heel stick, ear stick, or venipuncture.

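### Mailed T2 and T3 knowledge items can be checked against materials that only the two education arms receive, which could modestly inflate their contrasts with usual care

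*Combined protocol and SAP*

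**What the plan says.** All references are to the combined protocol and SAP.

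- **Mode.** Under Follow-up (T2) Assessment, telephone is the default: "The CRC will collect the data over the telephone and mark the answers on a paper survey for double data entry". If the woman cannot be reached, "the T2 survey will be mailed to the participant with a cover letter". Under Follow-up (T3) Assessment: "Reminder calls and a T3 survey mailing with cover letter [Attachment 13] will follow the procedures outlined for the T2 assessment".
- **Items.** The baseline survey description in Study Design and Methods lists two national-survey items (density as a risk factor, and masking) "as well as additional items derived from the written education materials". The same items are asked again at T2, and knowledge is reassessed at T3.
- **Who receives the materials.** The arms are defined at the start of the protocol as "usual care (standard density notification only), enhanced (standard density notification + written educational materials on breast density"), with the interpersonal arm receiving those same materials plus the promotora contact.
- **Analysis.** The Power Statement scores knowledge as the number correct of three key items. The Analytic Approach for Specific Aim 1 compares the score by pairwise Wilcoxon rank-sum tests at a threshold of 0.017. It has no term, stratification or sensitivity analysis for mode.
- **Conflicting text.** The data-management paragraph under Resources states "Administration of survey assessments (T1, T2, and T3) will occur by telephone and be interviewer-facilitated by the bilingual CRC". This leaves out the mail fallback.

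**The concern.** A woman who completes the survey alone on paper can look up an answer unobserved. If the item comes from the education materials, a woman in either education arm may have the source to hand, and a usual-care woman was never given it. Equal mail shares across arms would not cancel this, because the arms differ in what can be looked up and not in how often the survey is mailed. Randomisation does not remove it either.

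At stake is the interpretation of two of the three pairwise knowledge contrasts at each time point. A difference from usual care could partly reflect looking up rather than learning, in the direction the trial hypothesises for the interpersonal arm. The protocol itself regards mode as relevant to data quality: "an interviewer-facilitated mode of survey completion is preferred by patients over self-administered surveys and results in higher quality data".

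**Working it through.** **Reproducing the plan's figure.** The Noether formula for the rank-sum test with n per group is: detectable probability = 0.5 + (z for two-sided 0.017 + z for 80% power)/√(6n).

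- T2, n = 600: 0.5 + (2.387 + 0.842)/60 = 0.554, as stated.
- T3, n = 466: 0.5 + 3.228/52.88 = 0.561, as stated.

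The planned effect above the null is therefore 0.054 at T2 and 0.061 at T3.

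**Assumptions for the bias.** The documents give none of the following:

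- mail share m of 5-20% of completers;
- share f of mailed education-arm women who look up the item, 20-50%;
- one materials-derived item among the three, answered correctly when looked up;
- independent items with correct rates 0.5, 0.5 and 0.3 (the first two are close to the 49% and 53% in the national survey described under Background; the third is assumed);
- no true difference between arms.

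**Score distributions (0, 1, 2, 3 correct).**

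- Without look-up: 0.175, 0.425, 0.325, 0.075.
- With the third item looked up: 0, 0.25, 0.50, 0.25.

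The probability that a woman who looks up outscores one who does not, counting ties as half, is 0.25 × 0.3875 + 0.50 × 0.7625 + 0.25 × 0.9625 = 0.71875. A fraction m × f of the education arm looks up, so the shift from 0.5 is 0.21875 × m × f.

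**Test error.** The tie-corrected standard error is √[(1 − Σp³)/(6n)], where p are the score probabilities. With Σp³ = 0.117 this is 0.0157 at n = 600 and 0.0178 at n = 466. The false-positive rate is the two-sided normal rejection probability at 0.017, given the shift divided by this standard error.

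| Mail share | Looking up | Shift | T2 error (600/group) | T3 error (466/group) |
|---|---|---|---|---|
| 5% | 20% | 0.002 | 1.8% | 1.8% |
| 5% | one third | 0.004 | 2.0% | 1.9% |
| 5% | 50% | 0.005 | 2.4% | 2.2% |
| 10% | 20% | 0.004 | 2.1% | 2.0% |
| 10% | one third | 0.007 | 3.0% | 2.7% |
| 10% | 50% | 0.011 | 4.7% | 4.0% |
| 20% | 20% | 0.009 | 3.5% | 3.1% |
| 20% | one third | 0.015 | 7.3% | 5.9% |
| 20% | 50% | 0.022 | 16.1% | 12.4% |

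Seven of the nine T2 cells lie below 5%. The T3 column also requires that women still hold the materials about a year later.

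**Sensitivity to item rates.** At the extreme corner (m × f = 0.20 × 0.50 = 10%), the T2 error is 18.9% if all three items have rate 0.3, 8.2% at 0.49, 0.53 and 0.50, and 4.2% if all are 0.7.

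**The case against.** - **The attachments are not available.** The cover letters, scripts and survey forms are listed but not supplied. An answer-from-memory instruction, or a mode field, may already exist. This stands: neither can be called missing, and the first two steps of the fix begin with confirming.
- **The exposed item is not identified.** The three key items are not listed. A reader might infer that all three can be looked up in the education arms and none in usual care, which would make the bias much larger. The documents do not support that. Every arm receives the notification letter, and the introduction describes notification as dealing with density and its role in cancer risk, with mammogram sensitivity among the educational goals. The masking and risk items may therefore be equally open to look-up in usual care. One materials-derived item is the fair basis.
- **Mail is a last resort.** It follows failed telephone contact and is itself followed by further calls, so the share may be small. A telephone respondent could also consult the materials. Both points stand. Mail makes looking up easier and unobserved, but is not the only route.
- **The inputs are assumed.** Over much of the range the effect is close to nil, and only the extreme corner reaches 16%. Retention of the materials until T3 is inferred. The protocol's remark on data quality concerns mode in general and is not evidence of look-up.
- **The stakes are limited.** Anxiety is the primary Aim 1 outcome and knowledge is the second. Both education arms hold the materials, so their mutual contrast is not biased by this route unless mail use or look-up differs between them.

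What survives is the asymmetry itself, and an analysis plan that cannot show whether it mattered.

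**Conclusion.** The mechanism follows from the protocol's own text, and its size cannot be determined from it. With one item exposed and the assumed ranges, the T2 shift is 0.002 to 0.022, about 4% to 41% of the planned 0.054 (0.002/0.054 and 0.022/0.054). The pairwise false-positive rate is 1.8% to 16%, near 2-5% in most of the range. At T3 it is 1.8% to 12%, if women still have the materials.

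A reader might go further and conclude that a positive knowledge result against usual care would be an artefact. The documents do not support that: the shift is well below the planned effect throughout the range, and no look-up has been shown. The severity is minor. The point concerns two contrasts on a secondary outcome.

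**What to change.** 1. Confirm that the T2 and T3 cover letters and telephone scripts (Attachments 8, 10, 11 and 13) ask women to answer the knowledge items from memory, without consulting any papers. If not, add one line for surveys still to be sent.
2. Confirm that completion mode (telephone, mail, in person) is recorded for each T2 and T3 survey, and report it by arm.
3. In the Analytic Approach for Specific Aim 1, pre-specify a supportive knowledge analysis by mode, either a mode-stratified rank test or a telephone-only repeat. Keep the all-respondent test as the main analysis. If stratified, show the estimate within each mode, because combining strata does not remove an asymmetry inside the mail stratum.
4. Reconcile the telephone-only sentence under Resources with the T2 and T3 procedures.

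The cost is at most one line in letters and scripts, one data field and one extra analysis. The instruction helps only prospectively, and the document already provides for a later T4 survey, so T2 and T3 collection may be well advanced. Mode is determined after randomisation, and promotora calls in one arm could affect who is reached by telephone. The telephone-only subset is therefore selected, and its result can support the main test but not replace it.

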Subject ID, subject code or any other person-specific unique identifying number, characteristic or code that can link the subject to their medical data		
Dates: All elements of dates [month, day, and year] directly related to an individual, their birth date, date of death, date of diagnosis, etc. Note: Recording a year only is not a unique identifier.		
Social Security number		
Medical device identifiers and serial numbers		
Biometric identifiers, including finger and voice prints, full face photographic images and any comparable images		
Web Universal Resource Locators (URLs), Internet Protocol (IP) address numbers, email address		

Street address, city, county, precinct, zip code, and their equivalent geocodes	X	X
Phone or fax numbers	X	X
Account, member, certificate or professional license numbers, health beneficiary numbers		
Vehicle identifiers and serial numbers, including license plate numbers		
Check 'None' when none of the identifiers listed above will be recorded, maintained, or shared during the conduct of this study. (exempt category 4)	 None	 None

In all cases, "External" refers to our trained study team members at MPH. Information will not be shared with any other External entities.

Data Analysis

Power analyses and study endpoints are not required for minimal risk research, pilot or feasibility studies.

No statistical information. *If checked, please explain:*

Power Statement:

A total of 2,000 Latinas will complete baseline assessments and be randomized to one of three groups of breast density notification: usual care, enhanced, or interpersonal approaches (approximately 667 women per group) (see Figure 1). Applying a 10% attrition rate between enrollment and the first follow-up time point and an additional 20% after one year, we have planned for a sample size of 1,800 (2,000*0.90, 600 per group) for T2 measures and a sample size of 1,400 (2,000*0.70, 466 per group) for T3 measures.

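### Aim 1 compares the arms at T3 with stand-alone tests on women who have a T3 score, with 30% expected missing and no missing-data method stated

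*Combined protocol and SAP*

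**What the plan says.** The Power Statement starts from the number randomized: "A total of 2,000 Latinas will complete baseline assessments and be randomized to one of three groups of breast density notification". It then subtracts expected losses: "Applying a 10% attrition rate between enrollment and the first follow-up time point and an additional 20% after one year". This gives "a sample size of 1,800 (2,000*0.90, 600 per group) for T2 measures" and "a sample size of 1,400 (2,000*0.70, 466 per group) for T3 measures".

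The Analytic Approach for Specific Aim 1 defines the anxiety endpoint as percent change in STAI from baseline, calculated at each follow-up. On the test it says: "The percent change will be compared between the three notification study groups with pairwise t-tests at one month as well as at one year". Knowledge, scored 0 to 3, is compared by pairwise Wilcoxon rank-sum tests at the same two times. The threshold is 0.017 for each pair.

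The T3 paragraph of the Methods offers telephone contact, reminder calls, a mailed survey and a certified letter to all participants. It then adds one more route: "Study staff may also approach patients in clinic if they present to the mammography unit for screening". Women not reached are coded as non-responders. The document gives no missing-data assumption, longitudinal model, imputation, weighting, comparison of dropouts with responders, or sensitivity analysis.

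**The concern.** Anxiety is the primary outcome for Aim 1 and one year is a named test time, yet three women in ten are expected to have no T3 score. A percent change cannot be calculated without the follow-up score, so a stand-alone T3 t-test runs on responders only.

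Two things are at stake.

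- **Precision.** Women seen at T2 but not at T3 carry information about T3 that the T3 test does not use.
- **Bias.** If dropout is related to anxiety or knowledge, and related differently in different arms, the responders' contrast is no longer a fair comparison of the randomized groups. This trial has a specific route to that. In-clinic contact at T3 is open only to women who return for screening, and Aim 2 hypothesizes that the interpersonal arm will return more often. If that is right, T3 response could differ by arm through a behavior that may itself be related to anxiety or knowledge.

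With no method stated, the handling of 30% missing data is also left to be chosen after the data are seen.

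**Working it through.** **1. Reproduce the plan's figures.** Inputs from the Power Statement: SD 50 percentage points, type-I error 0.017 (taken as two-sided), power 80%, 600 per group at T2 and 466 at T3. The detectable difference is 50 × √(2/n) × (2.387 + 0.842).

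- T2, n = 600: 9.32 (stated 9.3).
- T3, n = 466: 10.57 (stated 10.6).

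The Wilcoxon figures, by Noether's formula, come to 0.554 and 0.561, as stated. The power figures are correct, and they use the expected number of responders at each time.

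**2. Count the women affected.** 2,000 × 0.90 = 1,800 at T2 and 2,000 × 0.70 = 1,400 at T3. If nobody who misses T2 returns at T3, 1,800 − 1,400 = 400 women have T1 and T2 but no T3.

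**3. Precision.** For monotone missing data and a normal model, the variance of an arm's T3 mean change using T2 is s² × [(1 − ρ²)/466 + ρ²/600]. Here ρ is the T2-T3 correlation of the change scores. Dividing by s²/466 gives 1 − ρ² × (1 − 466/600) = 1 − 0.223ρ². The documents give no ρ, so a range is assumed.

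| Assumed ρ | Variance cut | Effective n per group | Detectable difference | Power at 10.6 |
|---|---|---|---|---|
| 0 (as planned) | 0% | 466 | 10.6 | 80% |
| 0.3 | 2.0% | 476 | 10.5 | 81% |
| 0.5 | 5.6% | 494 | 10.3 | 83% |
| 0.7 | 10.9% | 523 | 10.0 | 85% |

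**4. Bias if dropout follows T2 level.** Everything here is assumed: STAI SD 12; correlations T1-T2 0.5, T2-T3 0.6, T1-T3 0.5; no true arm difference; 70/90 of women seen at T2 retained at T3; and, in one arm only, higher odds of dropout per SD of T2 anxiety. By simulation, that arm's responders shift as follows.

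| Odds ratio per SD | T3 mean | T1 mean | Change from baseline |
|---|---|---|---|
| 1.5 | −0.63 | −0.51 | −0.11 |
| 2 | −1.02 | −0.85 | −0.18 |

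Selection on T2 also selects on baseline, so most of the shift cancels in a change score. Regressing T3 on T1 and T2 and averaging over all women seen at T2 brings the T3 bias to about zero. That happens because dropout was made to depend on T2.

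**5. Bias if dropout follows T2 change.** Assumed: percent-change SD 50; retention 466/600; in one arm only, dropout odds 1.65 or 2.72 times higher per SD of T2 change. The T3 contrast is biased by the amounts below, against a detectable difference of 10.6.

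| Assumed ρ | Bias, percentage points | Actual error of a nominal 1.7% test |
|---|---|---|
| 0.3 | 1.5 to 2.8 | 3% to 6% |
| 0.5 | 2.6 to 4.7 | 6% to 17% |
| 0.7 | 3.8 to 6.7 | 11% to 37% |

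A likelihood estimate that uses T2 has bias near zero under this mechanism too.

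**The case against.** The strongest case for the plan has four parts.

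- **The lost women are not thrown away.** A reader might infer that their data are discarded altogether. They are not: percent change is calculated at each follow-up, so their T1 and T2 scores enter the T2 test. Only the T3 contrast leaves them out.
- **Responders-only analysis is inferred.** The plan defines no analysis set. This is true, but the inference is firm: the endpoint needs the T3 score, the power figures reproduce with the responder numbers, and no other method is given.
- **Dropout related to outcome is not enough to invalidate the test.** If it works identically in every arm, the comparison keeps its error rate when there is no true difference. Differential dropout is needed, and the documents make it plausible without showing that it will occur. Telephone and mail contact are offered to everyone; clinic contact is an optional addition.
- **The bias may be small.** A reader might quote the 0.6 to 1.0 point shift in the raw T3 mean from step 4. The plan tests change from baseline, as a percentage, and in that scenario raw change is off by only 0.1 to 0.2 points. The larger figures in step 5 need a different assumed mechanism.

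All four limit the size of the point. None supplies a method for the 30% expected to be missing.

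**Conclusion.** The point holds for the T3 contrasts of Aim 1. At T2 the expected loss is 10%. Aim 2 takes adherence from the EMR for all 2,000 women and does not depend on survey response.

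The precision loss is modest: about 2% to 11% of T3 variance for ρ of 0.3 to 0.7. The main issue is unaddressed bias. Its size cannot be fixed from the documents. It ranges from about 0.1 to 0.2 STAI points in change from baseline (dropout following T2 level in one arm, odds ratio 1.5 to 2 per SD, SD 12) to several percentage points of percent change (dropout following T2 change). These are illustrations under assumed correlations and odds ratios, not predictions.

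A reader might also infer that a repeated-measures model would remove dropout bias outright. It does so only if data are missing at random given what the model contains. If T3 response depends on return to clinic or on unseen T3 anxiety, T1 and T2 scores alone may not be enough. The change is worth making because it is cheap, uses data already being collected, and settles the handling of missing data in advance.

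**What to change.** 1. **Main anxiety analysis.** Model the STAI score at T2 and T3 in one repeated-measures model with arm, time, arm-by-time, baseline STAI and baseline-by-time, unstructured covariance, and all women with any follow-up. Take the pairwise arm contrasts at each time from it, at the 0.017 level. State openly that this replaces percent change with a baseline-adjusted difference in score.
2. **Multiple imputation.** Impute by arm, including T1, T2 and EMR return status, for T3 knowledge and as a supporting analysis for STAI. Return status follows randomization, so it belongs in the imputation model and not as a covariate in the arm comparison. Imputation can also bring in women with neither T2 nor T3, whom the repeated-measures model omits.
3. **Reporting.** Give T2 and T3 response by arm, and the mode of T3 contact including in-clinic approach.
4. **Sensitivity analyses.** Add a not-at-random delta-shift analysis that moves the imputed values, including by different amounts in different arms. Keep the planned responders' t-tests and Wilcoxon tests alongside.

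The cost is SAP wording and a little more analysis work, with no new data. The main analysis will rest on a missing-at-random assumption, which the delta-shift analysis is there to test.
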